12.1 Social impacts

It is possible that participants' involvement in the study could result in social impacts. Social harms are negative social impact events and social benefits are positive social impact events that a participant reports as affecting them as a result of being involved in a research study. It is not the researcher's opinion of how they perceive an event has affected a participant. For example, a participant's involvement in the study could become known to others, and a social harm may result (eg, participants could be perceived as having HIV or as having a high likelihood of acquiring HIV). Participants could be treated unfairly or could have problems being accepted by their families and/or communities. Alternatively, a social benefit may result (eg, a participant could feel good helping others).

Social impacts will be collected and reported on CRFs during scheduled visits (see Appendix H and Appendix I). Social harms are tabulated by the SDMC and are subjected to descriptive analysis. The goal is to reduce their incidence and enhance the ability of study staff to mitigate them when possible. Summary tables of social impact events will be generated weekly and made available for review by the protocol chairs, PTL, and the designated NIAID representative. A social harm that is reported by the participant and judged by the IoR/designee to be serious or unexpected will be reported to the responsible site's IRB at least annually, or according to their individual requirements.

In the event that a participant reports a social harm, every effort will be made by study staff to provide appropriate care and counseling to the participant as necessary, and/or referral to appropriate resources for the safety and well-being of the participant. If CRS staff have questions regarding ways to assist a participant dealing with a social impact, a designated NIAID or Network Core representative can be contacted. While maintaining participant confidentiality, study sites may engage their CAB in exploring the social context surrounding instances of social harms to minimize the potential occurrence of such an impact.

12.2 Emergency communication with study participants

As in all clinical research, this study may generate a need to reach participants quickly to avoid imminent harm, or to report study findings that may otherwise concern their health or welfare.

When such communication is needed, the CRS will request that its IRB/EC and any applicable RE expedite review of the message. If this review cannot be completed in a timeframe consistent with the urgency of the required communication, the CRS can contact the participant without IRB/EC approval if such communication is necessary to avoid imminent harm to the study participant. The CRS must notify the IRB/EC and any applicable RE of the matter as soon as possible.

13 Version history

The Protocol Team may modify the original version of the protocol. Modifications are made to Network protocols via clarification memos, letters of amendment, or full protocol amendments.

The version history of, and modifications to, Protocol HVTN 143/HPTN 109 are described below.

Protocol history and modifications

Date: June 07, 2023

Protocol version: 1.0 Protocol modification: Original protocol

14 Document references (other than literature citations)

Other documents referred to in this protocol, and containing information relevant to the conduct of this study, include:

- Assessment of Understanding. Accessible through the HVTN protocolspecific website.
- Current Centers for Disease Control (CDC) Guidelines.
 - Revised Recommendations for HIV Testing of Adults, Adolescents, and Pregnant Women in Health-Care Settings. Available at http://www.cdc.gov/mmwr/PDF/rr/rr5514.pdf.
 - Revised Guidelines for HIV Counseling, Testing, and Referral. Available at http://www.cdc.gov/mmwr/preview/mmwrhtml/rr5019a1.htm
- Division of AIDS (DAIDS) Clinical Research Policies and Standard Procedures Documents. Available at https://www.niaid.nih.gov/research/daids-clinical-research-policies-standardprocedures
- Division of AIDS Protocol Registration Manual. Available at https://www.niaid.nih.gov/sites/default/files/prmanual.pdf
- Division of AIDS Table for Grading the Severity of Adult and Pediatric Adverse Events. Corrected Version 2.1, July 2017. Available at https://rsc.niaid.nih.gov/clinical-research-sites/daids-adverse-event-gradingtables
- The Manual for Expedited Reporting of Adverse Events to DAIDS. Version 2.0, January 2010. Available at https://rsc.niaid.nih.gov/clinical-research-sites/manual-expedited-reporting-adverse-events-daids
- Common Terminology Criteria for Adverse Events (CTCAE), Version 5.0. Published November 27, 2017. Available at https://ctep.cancer.gov/protocoldevelopment/electronic_applications/docs/ctca e_v5_quick_reference_5x7.pdf
- HVTN Certificate of Confidentiality. Accessible through the HVTN website.
- HPTN Certificate of Confidentiality.
- HVTN 143/HPTN 109 Special Instructions. Accessible through the HVTN protocol-specific website.

- HVTN 143/HPTN 109 Study Specific Procedures. Accessible through the HVTN protocol-specific website.
- HVTN 143/HPTN 109 Site Lab Instructions. Accessible through the HVTN protocol-specific website.
- Ab Manual of Operations. Accessible through the HVTN website.
- Dangerous Goods Regulations (updated annually), International Air Transport Association. Available for purchase at https://www.iata.org/publications/dgr/Pages/index.aspx
- Lab assay algorithm (available upon request)
- International Council on Harmonisation of Technical Requirements for Pharmaceuticals for Human Use (ICH) E6, Guideline for Good Clinical Practice: Section 4.8, Informed consent of trial subjects. Available at http://www.ich.org/products/guidelines/efficacy/article/efficacyguidelines.html
- Participants' Bill of Rights and Responsibilities. Accessible through the HVTN website.
- National Institutes of Health (NIH) Policy on Reporting Race and Ethnicity Data: Subjects in Clinical Research. Available at https://grants.nih.gov/grants/guide/notice-files/NOT-OD-01-053.html
- Pharmacy Guidelines and Instructions for DAIDS Clinical Trials Networks, July 2008.
- Requirements for Source Documentation in DAIDS Funded and/or Sponsored Clinical Trials. Available at https://www.niaid.nih.gov/sites/default/files/score-source-documentationrequirements.pdf
- Title 21, Code of Federal Regulations, Part 50. Available at http://www.accessdata.fda.gov/scripts/cdrh/cfdocs/cfcfr/CFRSearch.cfm?CFR Part=50
- Title 45, Code of Federal Regulations, Part 46. Available at https://www.hhs.gov/ohrp/regulations-and-policy/regulations/45-cfr-46/index.html
- The Protection of Personal Information Act (POPIA, South Africa, 2013). Available at https://www.gov.za/sites/default/files/gcis_document/201409/3706726-11act4of2013protectionofpersonalinforcorrect.pdf

See Section 16 for literature cited in the background and statistics sections of this protocol.

15 Acronyms and abbreviations

λz	terminal elimination rate constant
Ab	antibody
ADA	antidrug antibody
ADCC	antibody-dependent cell-mediated cytotoxicity
ADCP	antibody-dependent cellular phagocytosis
AE	adverse event
AFAB	assigned female sex at birth
Alk Phos	alkaline phosphatase
ALT	alanine aminotransferase
AMAB	assigned male sex at birth
AMP	antibody-mediated prevention
ANOVA	analysis of variance
AoU	Assessment of Understanding
ART	antiretroviral therapy
ARV	antiretroviral
AST	aspartate aminotransferase
ATI	analytical treatment interruption
AUC	area under the curve
AUC-MB	area under the magnitude-breadth curve
BAMA	binding antibody multiplex assay
β-HCG	beta human chorionic gonadotropin
BIDMC	Beth Israel Deaconess Medical Center
bnAb	broadly neutralizing antibody
CAB	Community Advisory Board
CAVD	Collaboration for AIDS Vaccine Discovery
CBC	complete blood count
CC	Clinic Coordinator
CD4bs	CD4 binding site
CDC	US Centers for Disease Control and Prevention
CDM	Clinical Data Manager
CFR	Code of Federal Regulations
cGMP	current Good Manufacturing Practice
CAVD	Collaboration for AIDS Vaccine Discovery
СНО	Chinese hamster ovary
CI	confidence interval
CL	clearance
Cmax	maximum concentration
CRF	case report form

CRPMC	NIAID Clinical Research Products Management Center
CRS	clinical research site
CSR	central specimen repository
CSS	Clinical Safety Specialist
CTCAE	Common Terminology Criteria for Adverse Events
CTM	Clinical Trials Manager
DAERS	DAIDS Adverse Experience Reporting System
DAIDS	The Division of AIDS (US NIH)
DHHS	US Department of Health and Human Services
EAE	expedited adverse event
EC	Ethics Committee
eGFR	estimated glomerular filtration rate
ELISA	enzyme-linked immunosorbent assay
Env	HIV envelope protein
Fc	Fragment crystallizable
FcRn	neonatal Fc receptor
FDA	US Food and Drug Administration
FIH	first-in-human
FR3	Framework 3
Fred Hutch	Fred Hutchinson Cancer Center
GCP	Good Clinical Practice
GEE	generalized estimating equation
GLP	Good Laboratory Practice
GPL	immunoglobulin G phospholipid
GPP	Good Participatory Practices
HBsAg	hepatitis B surface antigen
HC	heavy chain
HCV	hepatitis C virus
HEp-2	human epithelial cell line
HPTN	HIV Prevention Trials Network
HSML-NICD	HIV Seromolecular Laboratory – National Institute for
	Communicable Diseases
HSV	herpes simplex virus type 2
HVTN	HIV Vaccine Trials Network
IAS-USA	International Antiviral Society – USA
IAVI	International AIDS Vaccine Initiative
IB	Investigator's Brochure
IC	inhibitory concentration
ICF	informed consent form

ICH	International Council for Harmonisation of Technical Requirements for Pharmaceuticals for Human Use
IgG	immunoglobulin G
IND	Investigational New Drug
IoR	Investigator of Record
IP	investigational product
IRB	Institutional Review Board
IRR	infusion-related reaction
IUD	intrauterine device
IV	intravenous
KI	knock-in
L	leucine
LC	HVTN Laboratory Center
LOC	HVTN Leadership and Operations Center
mAb	monoclonal antibody
MAR	missing at random
MB	magnitude breadth
MCAR	missing completely at random
MITT	modified intent-to-treat
MO	DAIDS Medical Officer
MOP	Manual of Operations
MTD	maximum tolerated dose
nAb	neutralizing antibody
NAEPP	National Asthma Education and Prevention Program
NHP	nonhuman primate
NIAID	National Institute of Allergy and Infectious Diseases (US NIH)
NIH	US National Institutes of Health
NSAID	nonsteroidal anti-inflammatory drugs
OD	optimal density
OHRP	US Office for Human Research Protections
PAB	DAIDS Pharmaceutical Affairs Branch
PCR	polymerase chain reaction
PD	pharmacodynamics
PI	Principal Investigator
PID	pelvic inflammatory disease
РК	pharmacokinetics
POPIA	Protection of Personal Information Act
popPK	population pharmacokinetic
РР	per-protocol

PrEP	pre-exposure prophylaxis
PSRT	Protocol Safety Review Team
PTL	Protocol Team Leader
RAB	DAIDS Regulatory Affairs Branch
RE	Regulatory Entity
RML	Regional Medical Liaison
RSC	DAIDS Regulatory Support Center
RSV	respiratory syncytial virus
S	serine
SAE	serious adverse event
SAHPRA	South African Health Products Regulatory Authority
SAIL-NICD	South African Immunology Laboratory – National Institute for Communicable Diseases
SAP	Statistical Analysis Plan
SC	subcutaneous
SCHARP	Statistical Center for HIV/AIDS Research and Prevention
SD	standard deviation
SDMC	HVTN Statistical and Data Management Center
SHIV	simian-human immunodeficiency virus
SICF	sample informed consent form
SMB	Safety Monitoring Board
SOP	standard operating procedures
SPT	DAIDS Safety and Pharmacovigilance Team
SSP	study-specific procedures
SST	serum-separating tube
STI	sexually transmitted infection
SUSAR	suspected unexpected serious adverse reaction
t1/2	half-life
ТВ	tuberculosis
TCR	tissue cross-reactivity
Tmax	time to maximum concentration
ULN	upper limit of normal
USP	United States Pharmacopeia
UW-VSL	University of Washington Virology Specialty Laboratory
VCMP	Vaccine Clinical Materials Program
Vd	volume of distribution
VRC	Dale and Betty Bumpers Vaccine Research Center (NIAID)
VRP	Vaccine Research Program

- ⁷ At an early-termination visit for a withdrawn or terminated participant who does not have HIV (see Section 9.10), blood should be drawn for HIV diagnostic testing, as shown for visit 8 above. If a participant has a confirmed diagnosis of HIV, do not collect blood for HIV diagnostic testing (see Section 9.12).
- ⁸ Urine testing is described in Section 9.7 and microscopy if needed.
- ⁹ Syphilis testing will be done by serology.
- ¹⁰ For participants with confirmed diagnosis of HIV, only specimens required for protocol-specified safety laboratory tests, urinalysis, and pregnancy tests will be collected.
- ¹¹ To investigate antibody (Ab)-administration-related clinical reactions, assays may be performed on serum samples taken prior to the study-product administration associated with the reaction and collected after the onset of reaction. Refer to the study-specific procedures (SSP) for more information.
- ¹² Serum-separating tube (SST) blood will be collected at specific timepoints after the onset of any Ab reaction. Refer to the SSP for more information.
- ¹³ The 56-day total blood volume does not include up to 34 mL SST blood collected for any Ab reaction; however, the 56-day limit is not exceeded at any visit by the possible collection of SST blood for an Ab reaction.
- ¹⁴ 8.5 mL of SST blood will be collected post-study-product administration (see SSP for details).
- ¹⁵ Pregnancy test at enrollment does not need to be performed if negative results are received from screening pregnancy test conducted within 48 hours prior to study-product administration.
- y = SST blood collected for serum storage will also cover specimen needs for drug concentrations, HIV-1 neutralizing Ab assays, non-neutralizing antiviral assays, and antidrug antibody (ADA) detection and functional assays (including for any Ab reactions); no separate blood draw is needed. The SST blood for Serum storage is collected prior to study product administration.

Appendix G Laboratory procedures for Part B

				11:- 4	4		-			-	7 -	0	•	40	44	40
				Visit	1 Screening	2	3	4	5	6		8	9	10	11	12
				Day:	visit ³	D1	D4	D7	D29	D57	D113	D169	D173 ¹⁶	D225	D304	D365
				Week:		W0			W4	W8	W16	W24		W32	W40	W48
						Study Product Administration #1					000000000000000000000000000000000000000	Study Product Administration #2				
				Tube size		VRC01.23LS +						VRC01.23LS +	1			
		Assay	Tube	(vol.		PGT121.414.LS +						PGT121.414.LS +				
Procedure	Ship to ¹	location ²	Type⁴	capacity)4		PGDM1400LS						PGDM1400LS				
BLOOD COLLECTION																-
Screening/Diagnostic																
Screening HIV test	Local lab	Local lab	EDTA	5mL	5	_	—	—	—	—	—	_	I —	_	—	_
HBsAg/anti-HCV	Local lab	Local lab	SST	5mL	5		—	—	—	—	—		—	—	—	—
Syphilis ⁹	Local lab	Local lab	SST	5mL	5	—	_	—	_	—	—	_	_		_	
HIV diagnostics ⁷	HSML-NICD	HSML-NICD	EDTA	10mL	—	—	-	—	—	—	10	_		10	—	10
Safety labs ¹⁰																
CBC/ Differential	Local lab	Local lab	EDTA	5mL	5	5	—	—	—	5	—	5	I —	5	_	5
Chemistry Panel ⁵	Local lab	Local lab	SST	5mL	5	5	-	—	—	5	—	5	—	5	—	5
Drug concentrations/detection							.,		,							
VRC01.23LS, PGT121.414.LS and PGDM1400LS concentration	CSR	HVTN Labs	SST	8.5mL	_	у	У	у	У	у	у	у	_	у	у	у
1 hour Post Study Product Administration VRC01.23LS, PGT121.414.LS and PGDM1400LS concentration ¹⁴	CSR	HVTN Labs	SST	8.5mL	_	8.5	_		_		_	8.5	_	_	_	
Humoral assays																
HIV-1 neutralizing Ab	CSR	HVTN Labs	SST	8.5mL	_	у	у	у	у	у	у	у	—	у	у	у
Non-neutralizing antiviral assays ¹⁷	CSR	HVTN Labs	SST	8.5mL	_	у	у	у	у	у	у	У	—	у	у	у
Anti-Drug Antibody (ADA)																
ADA detection assays (screening, confirmatory, titration)	CSR	HVTN Labs	SST	8.5mL	_	У	_	—	-		у		_	_	у	у
ADA functional assay	CSR	HVTN Labs	SST	8.5mL	_	y					y	—	—		y	y
Ab Reaction ¹¹							*******	£			×	5				h
Tryptase / C3 and C4 Complement / Cytokines	CSR	ARUP	SST	8.5mL	_					S	See foo	tnote 12				
ADA detection assays (screening, confirmatory, titration)	CSR	HVTN Labs	SST	8.5mL	_	See footnote y	_		—	_	—	See footnote y	_	_	_	—
ADA functional assay	CSR	HVTN Labs	SST	8.5mL	—	See footnote y	—	—	—	—	—	See footnote y	—	—	—	—
STORAGE	****															
Serum	CSR	_	SST	8.5mL		68.0	42.5	42.5	42.5	42.5	42.5	42.5		42.5	42.5	42.5
Visit total					25	86.5	42.5	42.5	42.5	52.5	53	61.0	0	62.5	42.5	62.5
56-Day total ¹³					25	112	154	197	239	292	53	114	61	124	105	168
																ļ
Urine dipstick ⁸	Local lab	Local lab			Х					Х	 	_				X
Pregnancy test ⁶	Local lab	Local lab			Х	X ¹⁵		—		—	I —	Х	I —	—	—	X

Footnotes for Appendix G:

¹CSR = central specimen repository; HSML-NICD = HIV Seromolecular Laboratory-National Institute for Communicable Diseases (Johannesburg, South Africa)

² HVTN laboratories include: Duke University Medical Center (Durham, North Carolina, USA); South African Immunology Laboratory-National Institute for Communicable Diseases (SAIL-NICD, Johannesburg, South Africa); Dartmouth College (Hanover, New Hampshire, USA).

Non-HVTN laboratories include: ARUP Laboratories (Salt Lake City, Utah, USA)

³ Screening may occur over the course of several contacts/visits, up to and including day 1 prior to study-product administration.

⁴ Local labs may assign appropriate alternative specimen type or tube types for locally performed tests.

⁵ Chemistry panels are defined in Section 9.2 (pre-enrollment), and Sections 9.3 and 9.4 (enrollment and follow-up).

⁶ For participants who are of pregnancy potential, pregnancy test must be performed on urine or blood specimens on the day of study-product administration with negative results received prior to administration. Persons who are NOT of pregnancy potential due to having undergone hysterectomy or bilateral oophorectomy (verified by medical records) are not required to undergo pregnancy testing.

⁷ At an early-termination visit for a withdrawn or terminated participant who does not have HIV (see Section 9.10), blood should be drawn for HIV diagnostic testing, as shown for visit 12 above. If a participant has a confirmed diagnosis of HIV, do not collect blood for HIV diagnostic testing (see Section 9.12).

⁸ Urine testing is described in Section 9.7 andmicroscopy if needed.

⁹ Syphilis testing will be done by serology.

¹⁰ For participants with confirmed diagnosis of HIV, only specimens required for protocol-specified safety laboratory tests, urinalysis, and pregnancy tests will be collected.

¹¹ To investigate antibody (Ab)-administration-related clinical reactions, assays may be performed on serum samples taken prior to the study-product administration associated with the reaction and collected after the onset of reaction. Refer to the study-specific procedures (SSP) for more information.

¹² Serum-separating tube (SST) blood will be collected at specific timepoints after the onset of any Ab reaction. Refer to the SSP for more information.

¹³ The 56-day total blood volume does not include up to 51 mL SST blood collected for any Ab reaction; however, the 56-day limit is not exceeded at any visit by the possible collection of SST blood for an Ab reaction.

¹⁴ 8.5 mL of SST blood will be collected post-study-product administration (see SSP for details).

¹⁵ Pregnancy test at enrollment does not need to be performed if negative results from screening pregnancy test are received prior to study-product administration on the day of study-product administration.

¹⁶ Phone contact only. No specimen collection at this visit.

y = SST blood collected for serum storage will also cover specimen needs for drug concentrations, HIV-1 neutralizing Ab assays, non-neutralizing antiviral assays, and antidrug antibody (ADA) detection and functional assays (including for any Ab reactions); no separate blood draw is needed. The SST blood for Serum storage is collected prior to study product administration.

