4.3 Preclinical studies

4.3.1 Preclinical studies of VRC01.23LS

A summary of nonclinical studies conducted with VRC01.23LS is presented in the table below.

Study purpose	Study Outcome		
In vitro neutralization activity (Section 4.3.1.1)	On a 208 HIV-pseudovirus cross-clade panel, in comparison to VRC01, VRC01.23LS exhibits an overall ~8-fold greater neutralization potency with a geometric mean IC50 of 0.042 mcg/mL, and 94% breadth at IC50 of < 1 mcg/mL.		
VRC01.23LS serum levels in	In human FcRn transgenic mice, VRC01.23LS exhibited a		
Mice (Section 4.3.1.2)	serum t1/2 comparable to that of parental VRC01LS.		
NHP PK (Section 4.3.1.3)	Three cynomolgus monkeys received a single IV dose of 10 mg/kg VRC01.23LS. Two of the monkeys exhibited PK comparable to that of parental VRC01LS. One monkey exhibited depletion beginning on day 20, suggesting induction of an antidrug antibody (ADA) response. No signs of toxicity were observed.		
Tissue cross-reactivity (TCR) study (Section 4.3.1.4)	In a Good Laboratory Practice (GLP) TCR study evaluating a panel of 38 normal human tissues obtained from at least 3 adult donors per tissue, VRC01.23LS did not exhibit specific cell membrane binding in any human tissue, which was expected and was consistent with similar lack of binding observed for VRC01 and VRC01LS.		
Autoreactivity by assessment of binding to a human epithelial cell line (HEp-2) by indirect immunohistochemistry (Section 4.3.1.5)	VRC01.23LS demonstrated no evidence of autoreactivity as assessed by HEp-2 cell binding.		
Autoreactivity by assessment of anti-phospholipid reactivity	VRC01.23LS was considered not reactive in the cardiolipin binding assay when compared to an anti-HIV neutralizing		
(Section 4.3.1.6)	mAb (4E10), known to react with phospholipids.		

Table 4-1 Nonclinica	I studies condu	cted with VRC01.23LS
-----------------------------	-----------------	----------------------

4.3.1.1 In Vitro Neutralization Activity.

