5.2 Secondary objectives and endpoints

Secondary objective 1:

To correlate serum concentrations of VRC01.23LS, PGT121.414.LS, and PGDM1400LS with corresponding virus neutralization titers in serum

Secondary endpoints 1:

- Serum concentrations of VRC01.23LS, PGT121.414.LS, and PGDM1400LS at prespecified timepoints for all participants in all groups regardless of how many product administrations and how much product they received
- Magnitude of serum neutralizing activity measured with Env-pseudotyped viruses in TZM-bl cells at prespecified timepoints for all participants in all groups regardless of how many product administrations and how much product they received

Secondary objective 2:

To determine whether the mAbs maintain their expected combined magnitude and breadth of serum neutralizing activity after each 3-mAb administration as predicted by the known magnitude and breadth of neutralization of the corresponding mAb combinations as noninfused clinical products

Secondary endpoint 2:

Magnitude of neutralizing activity against a panel of Env-pseudotyped reference viruses in TZM-bl cells at selected timepoints for all participants in all groups regardless of how many product administrations and how much product they received

Secondary objective 3:

To determine whether ADAs are present and whether there is a correlation among VRC01.23LS, PGT121.414.LS, and PGDM1400LS concentrations and ADA titers in serum samples

Secondary endpoint 3:

Serum VRC01.23LS, PGT121.414.LS, and PGDM1400LS concentrations and ADA titers in each group measured at prespecified timepoints for all participants in all groups regardless of how many product administrations and how much product they received

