10.7 Ab reaction assays

To investigate Ab reactions, serum samples collected after the onset of reaction may be tested to measure levels of certain markers (eg, tryptase, complement components [C3 and C4], and cytokines). ADA detection and functional assays, as described above, may be performed on serum samples taken prior to the study-product administration associated with the reaction. Refer to the HVTN 143/HPTN 109 SSP for more information.

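### Part B has no routine ADA test on the Day 169 serum drawn before infusion 2, so ADA first seen at Day 304 or later cannot be placed before or after the second dose

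*Protocol*

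**What the plan says.** The ADA objective for the trial is secondary objective 3 (Protocol 5.2): "To determine whether ADAs are present and whether there is a correlation among VRC01.23LS, PGT121.414.LS, and PGDM1400LS concentrations and ADA titers". Protocol 10.5 sets up tiered testing (screening, then confirmation, then titration) at the timepoints indicated in the schedule, and 10.6 adds a functional assay for positives.

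Appendix G gives the Part B schedule. The rows for "ADA detection assays (screening, confirmatory, titration" and for "ADA functional assay" are both marked at D1, D113, D304 and D365. At D169, the day of infusion 2, the routine detection cell is empty and the functional cell holds a dash.

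ADA does appear at D169 in the block for antibody reactions, where the cell reads "See footnote y". Footnote 11 of Appendix G ties that block to the work-up of a reaction and says that "assays may be performed on serum samples taken prior to the study-product administration associated with the reaction and collected after the onset of reaction". Protocol 10.7 likewise says that ADA assays "may be performed on serum samples taken prior to the study-product administration associated with the reaction".

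Serum is nevertheless drawn at D169 from everyone. Appendix G lists 42.5 mL for storage, and footnote y says that this tube also serves the ADA assays without a separate draw. On timing it states: "The SST blood for Serum storage is collected prior to study product administration".

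**The concern.** D169 closes the first dosing interval and opens the second. It is the one visit whose pre-infusion serum shows which ADA was present before re-dosing. Without a scheduled result there, three things are lost.

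- **Timing.** A participant negative at D113 and positive at D304 may have developed ADA late in the first interval or after the second dose, and the scheduled data cannot tell these apart.
- **Reactions.** If D169 serum is tested only in participants who react, ADA status at infusion 2 is known for reactors and unknown for the non-reactors with whom they should be compared.
- **Pairing.** Secondary objective 3 relates concentrations to ADA titers. Concentrations are measured at D169 in all Part B participants, but no ADA result stands beside them. The exploratory work on ADA and PK foreseen in Protocol 6.4.6 also lacks ADA status at the start of the second interval.

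**Working it through.** **1. Reading the schedule.** Appendix G has 12 visit columns. Matching each row's 12 cells to them gives:

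| Row | Visits marked |
|---|---|
| mAb concentration, pre-dose or visit sample | D1, D4, D7, D29, D57, D113, D169, D225, D304, D365 |
| ADA detection, routine | D1, D113, D304, D365 |
| ADA functional, routine | D1, D113, D304, D365 |
| ADA detection and functional, reaction block | D1, D169 |

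The two routine ADA rows agree on all four visits, and the functional row has an explicit dash at D169. The empty detection cell is therefore unlikely to be an artefact of reading the table from PDF.

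**2. Confirming that the serum is there.** The D169 volumes are CBC 5, chemistry 5, post-infusion concentration 8.5 and storage 42.5: 5 + 5 + 8.5 + 42.5 = 61.0 mL, which is the visit total in Appendix G. Adding D113 (10 + 42.5 = 52.5) gives 52.5 + 61.0 = 113.5 mL, shown as the 56-day total of 114. A routine ADA test on the stored serum leaves both totals unchanged.

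**3. Gaps between routine ADA results (nominal days).**
- D113 to infusion 2: 169 − 113 = 56 days.
- Infusion 2 to the next routine ADA test: 304 − 169 = 135 days (D225 is not marked either).
- D113 to D304: 304 − 113 = 191 days without a routine ADA result.

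Appendix K allows ±7 days at D113 and ±14 days at infusion 2. The first gap can therefore run from (169 − 14) − (113 + 7) = 155 − 120 = 35 days to (169 + 14) − (113 − 7) = 183 − 106 = 77 days.

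**4. What each pattern allows, for a participant negative at D1.**

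| D113 | D304 or D365 | As scheduled | With D169 marked |
|---|---|---|---|
| positive | any | arose after dose 1 | same |
| negative | negative | no ADA seen at scheduled tests | also checked at trough |
| negative | positive | dose 1 (late) or dose 2, unresolved | D169 positive: before dose 2; D169 negative: first seen after dose 2 |

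Only the last row is ambiguous.

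**5. Pairs for secondary objective 3.** Between baseline and re-dosing there is one visit with both a concentration and an ADA result (D113). Marking D169 makes it two and adds the trough.

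**6. Size of the change.** Planned Part B enrolment is 4 × 8 + 30 = 62, so at most 62 further tier-1 screens per antibody, or 62 × 3 = 186 in all.

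**The case against.** The strongest reply is that this is a scheduling choice and not an error. The protocol does not contradict itself, and secondary objective 3 asks about the presence of ADA and its correlation with concentrations. It does not ask for attribution by dose or prediction of reactions. Serum is stored at D169, and again at D225. Protocol 10.10 keeps specimens indefinitely unless a participant, ethics committee or regulator requires otherwise, so the missing result could be produced later. All of this stands, and it limits the weight of the point. It does not remove it: testing chosen after reactions have been seen is weaker than a fixed timepoint, and an analysis plan cannot supply an assay result that the schedule does not generate.

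A reader might also infer more than the documents support:

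- *That ADA cannot be assigned to either dose, or that its link with second-infusion reactions cannot be studied.* D113 falls after dose 1 and before dose 2 in every participant, so earlier ADA can be assigned, and reactors and non-reactors alike have that result.
- *That the stretch from D113 to D304 has no samples.* It is untested, not unsampled.
- *That the share of those days lying before infusion 2 measures misattribution.* It counts calendar days. It would describe ADA only if onset were uniform over the period, which nothing in the protocol supports. Nor does any text say that ADA first seen at D304 will be credited to dose 2.
- *That the animal data point to this window.* For VRC01.23LS, Table 4-1 reports: "One monkey exhibited depletion beginning on day 20, suggesting induction of an antidrug antibody (ADA) response". The mice given PGT121.414.LS lost drug after day 9 (4.3.2.1), and none of the six rhesus macaques given that antibody developed ADA (4.3.2.2). The losses attributed to ADA were early, so they do not show a risk between D113 and D169.

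**Conclusion.** The point holds in a limited form. Routine Part B ADA testing omits the pre-infusion-2 trough. As a result, ADA negative at D113 and first positive at D304 or later cannot be placed in the last 56 days of the dose-1 interval (35 to 77 with windows) or after dose 2. Any D169 comparison of reactors with non-reactors would lack the non-reactors, and the D169 concentration has no ADA partner. How many participants this affects cannot be stated, because the protocol gives no expected ADA incidence or onset time.

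Secondary objective 3 remains answerable, with less information. This is a worthwhile, cheap improvement to a secondary objective, not a threat to the primary analyses.

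Two assumptions matter. The Appendix G cells are read as described above. The benefit also presumes that the ADA assays can detect ADA at the drug levels present at D169; the protocol gives no drug-tolerance figure, so a negative D169 result would make ADA before dose 2 less likely without excluding it.

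**What to change.** In Appendix G, mark ADA detection at D169 for all Part B participants, on the stored serum drawn before infusion 2. Apply the tiers of Protocol 10.5 and the functional assay of 10.6 to positives only. Keep D113: it is the only other routine ADA test between baseline and re-dosing, and dropping it could miss transient ADA. Summarise ADA as present before dose 2 (with D1 positives shown separately) versus first seen after dose 2.

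The cost is at most 62 tier-1 screens per antibody plus confirmatory, titration and functional tests on positives. No blood, tube or visit is added.
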